1. PROTOCOL SUMMARY

1.1. Synopsis

Protocol Title: A Phase 2b, randomized, double-blind, placebo-controlled, dose-ranging, multi-center study to evaluate the efficacy and safety of GB001 as maintenance therapy in adult subjects with moderate to severe asthma

Short Title: GB001 in adult subjects with moderate to severe asthma

Rationale:

GB001 is a potent and highly selective oral prostaglandin D₂ receptor (DP₂) antagonist. DP₂ is expressed on a variety of cells implicated in the allergic process including eosinophils and epithelial cells (Kupczyk, 2017; Singh, 2017). GB001 is being developed as a once daily oral add-on maintenance treatment for moderate to severe eosinophilic asthma.

The purpose of this Phase 2b study is to evaluate the efficacy, safety, pharmacokinetics, and pharmacodynamics of 3 GB001 dose levels compared with placebo in subjects with moderate to severe asthma and an eosinophilic phenotype. The study will assess the efficacy of GB001 relative to placebo in reducing asthma worsening when added to standard of care (SOC) asthma maintenance therapy.

Objectives and Endpoints (Primary and Secondary):

Objectives	Endpoints
Primary	

 • To evaluate the effect of GB001 compared to placebo on reducing asthma worsening 	
 • The proportion of subjects who experience worsening of asthma by Week 24 as defined by at least one of the following: 
 ○ On 2 consecutive days, morning (AM) peak expiratory flow (PEF) \leq 75% of mean AM PEF measured over the last 7 days of the Run-in ○ Forced expiratory volume in 1 second (FEV₁) < 80% of baseline (Visit 2) ○ Increase in rescue medication use of \geq 6 puffs/day on 2 consecutive days compared to mean use over the last 7 days of the Run-in ○ Increase in Asthma Control Questionnaire (ACQ-5) score of \geq 0.5 compared to baseline (Visit 2) ○ The occurrence of a severe asthma exacerbation (asthma attack) defined as deterioration of asthma that leads to the use of systemic corticosteroids for at least 3 days, hospitalization, or an Emergency Department visit
Secondary	

 • To evaluate the effects of GB001 compared with placebo on a range of clinical endpoints, including change in ACQ-5 score, change in pulmonary function, and time to first asthma worsening event 	
 • Change from baseline to Week 24 in ACQ-5 score • Change from baseline to Week 24 in pre-bronchodilator FEV₁ • Time to first asthma worsening • Annualized rate of severe asthma exacerbations • Change from baseline to Week 24 in post-bronchodilator FEV₁ • Change from baseline to Week 24 in AM PEF

 • To evaluate the safety and tolerability of GB001 compared with placebo 	
 • Incidence of treatment-emergent adverse events (TEAEs) • Change from baseline in laboratory, vital signs, and electrocardiogram (ECG) parameters

Overall Design:

This is a Phase 2b, randomized, double-blind, placebo-controlled, dose-ranging, multi-center study to evaluate the efficacy and safety of GB001 as maintenance therapy in a moderate to severe eosinophilic asthma population. GB001 will be added to the subject's standard-of-care asthma treatment.

An interim analysis to inform further development of GB001 will be conducted after the first 320 subjects have completed the study or have prematurely withdrawn from the study.

A schematic of the study design is presented in [Section 1.2](#).

Disclosure Statement:

This is a parallel group treatment study with 4 arms that is participant, Investigator, and Sponsor blinded.

Number of Participants:

This study will randomize approximately 480 subjects, with approximately 120 subjects per treatment group.

Intervention Groups and Duration:

[figure not shown]
Treatment groups:

- GB001 60 mg daily
- GB001 40 mg daily
- GB001 20 mg daily
- Matching placebo daily

Total duration for study participation per subject is up to 34 weeks (includes a Screening visit; followed by a 2-week to 6-week Run-in period to allow for collection of baseline eDiary data; a 24-week Double-Blind, Placebo-Controlled period; and 4-week Follow-up period).

Independent Data Monitoring Committee (IDMC): Yes

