1.2. Schema

1.3. Schedule of Activities

Procedure	Screening Visit	Randomization	Double-Blind, Placebo-Controlled Period Visit Window is ± 2 days									Early Discontinuation of IP	Early Withdrawal from Study	Follow-up (after W24 or 4 weeks after EW from study)	Notes	
			Visit 1	2	2.5	3	3.5	4	5	6	7					8
Week	-6 to -2	0	1	2	3	4	8	12	16	20	24	If needed	If needed	28		
Written informed consent	X*															*May be obtained prior to Visit 1
Demography	X															
Medical history	X															Including atopic conditions
Asthma and exacerbation history	X															Including triggers
Asthma treatment history	X															
Smoking history	X															
Concomitant medication	X	X	X	X	X	X	X	X	X	X	X	X	X	X	X	Including SOC asthma treatment
Complete physical examination	X										X	X	X			Including height and weight. Conduct prior to spirometry.
Vital signs	X	X	X	X	X	X	X	X	X	X	X	X	X	X	X	
12-lead electrocardiogram	X								X		X	X	X			Prior to spirometry
Fractional exhaled nitric oxide	X	X								X		X	X			Prior to spirometry. Prior to exhaled breath condensate analysis, if performed. See Section 8.6.2 .
Exhaled Breath Condensate Analysis		X*										X	X			May be collected at sites that are properly trained and qualified. Prior to spirometry. *Exhaled breath condensate analysis may be conducted on the next calendar day. See Section 8.6.7 .
Spirometry pre-bronchodilator	X	X				X	X	X	X	X	X	X	X	X	X	
Spirometry post-bronchodilator	X										X	X				After 4 puffs albuterol/salbutamol
Inclusion/exclusion criteria	X															
Randomization criteria		X														
Asthma Control Questionnaire-5	X	X		X		X	X	X	X	X	X	X	X	X	X	

Procedure	Screening Visit	Randomization	Double-Blind, Placebo-Controlled Period Visit Window is ± 2 days									Early Discontinuation of IP	Early Withdrawal from Study	Follow-up (after W24 or 4 weeks after EW from study)	Notes
			Visit 1	2	2.5	3	3.5	4	5	6	7				
Week	-6 to -2	0	1	2	3	4	8	12	16	20	24	If needed	If needed	28	
Asthma Quality of Life Questionnaire- (Standardized)		X									X	X	X		
Sino-Nasal Outcome Test-22		X									X	X	X		Only in subjects with a history of sinusitis or allergic rhinitis
Hair loss assessment		X									X	X	X		See Section 8.1.7
Pregnancy test (women of child-bearing potential only)	S	U		U		U	U	U	U	U	U	U	U	U	S = Serum U = Urine. If urine is positive, collect serum to confirm.
Hematology with differential	X	X*				X		X			X	X	X	X	See Appendix 2 (Section 10.2) *Includes INR at Visit 2.

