4.1.1. Study Design

The study will commence with a Screening visit (Visit 1), at which informed consent will be obtained and inclusion and exclusion criteria will be assessed. Informed consent may be obtained prior to the day of the Screening visit to allow for medication washouts or for other logistical reasons such as obtaining documentation of exacerbations or historical reversibility, if necessary. All other screening procedures should be completed on the day of the Screening visit. Subjects not meeting the eligibility criteria will be deemed screen failures and will not continue participation in the study (see [Section 5.4](#)). Eligible subjects will enter a Run-in period of a minimum of 2 weeks and a maximum of 6 weeks and will remain on their SOC regimen. The Run-in period commences with completion of all Screening visit procedures and concludes at the Randomization visit. During the Run-in period, subjects will capture PEF and asthma symptoms in an eDiary daily. Subjects who experience an asthma exacerbation during the Run-in period will receive appropriate treatment and remain in the Run-in period until their asthma status has returned to baseline status for at least 1 week. Subjects who are not able/eligible to be randomized due to ongoing asthma exacerbation at the end of the Run-in period will be discontinued from study participation and be labeled as Run-in failures. Subjects will remain on their SOC therapy during the Run-in period.

At Visit 2 (Week 0, Day 1), subjects who meet the randomization eligibility criteria will be randomized in a 1:1:1:1 ratio to receive one of the following double-blind treatments for 24 weeks:

- GB001 60 mg daily
- GB001 40 mg daily
- GB001 20 mg daily
- Matching placebo daily

Randomization will be stratified by baseline ICS dose (medium or high, as defined in Appendix 10; [Section 10.10](#)) and country.

The first dose of double-blind investigational product (IP) will be administered in the clinic on Day 1. All subsequent doses will be taken orally at home at bedtime on an empty stomach.

Following initiation of IP, subjects will visit the clinic for assessments at Weeks 2, 3, and 4, followed by visits approximately every 4 weeks for an additional 5 visits. Subjects should remain on their stable current SOC therapy (ie, medium or high dose ICS plus additional controller therapy) through the duration of their time on study (refer to Schedule of Activities, [Section 1.3](#)).

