Randomization Visit (Visit 2): All procedures should be completed on the same day. Sputum induction and Exhaled Breath Condensate may be conducted on the next calendar day when necessary, followed by the first dose in clinic and post PK sample. Randomization should be performed on the day of first dose in clinic. (List is not all inclusive. Review the SoA and the Study Reference Manual for additional guidance.)

- Download the eDiary and check if today's diary has been completed
- Review eDiary to assess eligibility
- Review randomization eligibility criteria
- Have subject complete questionnaires
- Exacerbation review
- Concomitant medications and adverse event review
- Vital signs
- FeNO
- Exhaled breath condensate (EBC) analysis (only at select sites that are properly trained and qualified)
- Spirometry (pre-bronchodilator only)
- Collect lab samples and predose PK sample
- Sputum induction (only at select sites that are properly trained and qualified)
- Register visit in the eCRF
- Ensure subject has a rescue inhaler

- Dispense IP
- Collect post-dose PK sample at 2.5 hours post-dose
- Complete eCRF

Other visits when these procedures are part of the visit:

- Have the subject complete questionnaires
- Vital signs
- ECG
- FeNO
- EBC analysis (only at select sites that are properly trained and qualified)
- Spirometry (pre-bronchodilator only)
- Collect lab samples and predose pharmacokinetic sample
- Sputum induction (only at select sites that are properly trained and qualified)

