8.1.3. Pulmonary Function Testing including Reversibility

Pre-albuterol/salbutamol morning FEV₁ will be measured using electronic spirometry between 5:00 AM and 12:00 noon and within ± 1 hour from the time of the Screening visit FEV₁ measurement time. Spirometry will be measured at all visits except Visit 3. Subjects should withhold short-acting beta-agonist (SABA) use for ≥ 6 hours prior to measurement of spirometry, long-acting beta-agonists (LABAs) for ≥ 12 hours prior to spirometry and ultra-LABA (eg, vilantrol) > 24 hours prior to spirometry. Additionally, forced vital capacity (FVC), FEV₁/FVC, PEF and forced expiratory flow at 25% to 75% (FEF₂₅₋₇₅) will be recorded. For predicted values, the Global Lung Initiative will be used. Additional details for pulmonary function testing will be available in the Study Reference Manual.

Reversibility

At the Screening visit, reversibility in FEV₁ will be measured before and within 30 minutes (± 15 minutes) of albuterol/salbutamol 360/400 μg via metered dose inhaler (MDI) or one nebulized treatment of albuterol/salbutamol. The subject must improve by at least 12% in FEV₁ to be eligible to enter the Run-in period. If the target is not met, historical documentation of reversibility in the 24 months prior to Screening visit or historical documentation of airway hypersensitivity may be allowed upon review and approval by the Medical Monitor.

Reversibility in FEV₁ will also be assessed at Visit 9 (Week 24) or the Early Discontinuation of IP visit.

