8.3.2.1. Change from Baseline to Week 24 Endpoints

Change from baseline to Week 24 in ACQ-5 score, pre-bronchodilator FEV₁, postbronchodilator FEV₁, and AM PEF will be analyzed as described below. The ACQ-5 is a five-item questionnaire which has been developed as a measure of the subject's asthma control that can be quickly and easily completed (Juniper E. F., 2005). The response options for each of these questions consists of a zero (no impairment/limitation) to 6 (total impairment/limitation) scale with the total score ranging from 0 to 30. ACQ-5 score is the average of the 5 non-missing items and will be calculated at each visit for each subject. The minimal clinically important difference (MCID) is 0.5 points.

For AM PEF, the baseline value is defined as the mean over the last 7 days of the Run-in including the value on Day 1 and Week 24 is defined as the mean over the last 7 days prior to Week 24 including the value on the day of the Week 24 visit. For the other endpoints, the baseline value is defined as the last non-missing value on or before the date of the first dose of study treatment.

If the number of subjects overall with a missing change from baseline value is < 5% for a particular endpoint:

- The primary analysis will be analysis of covariance (ANCOVA) without MI.
- As a sensitivity analysis, mixed-effects model with repeated measures (MMRM) without MI will also be performed.

If the number of subjects overall with a missing change from baseline value is \geq 5% for a particular endpoint:

- The primary analysis will be ANCOVA with MI.
- As sensitivity analyses, MMRM with MI, ANCOVA without MI, and MMRM without MI will also be performed.

Post-bronchodilator FEV_1 will not be analyzed using MMRM as it is collected at only one post-baseline timepoint.

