Each secondary endpoint of change from baseline to Week 24 will be analyzed using ANCOVA models. For this analysis, the MI procedure analogous to that described in Section 8.3.1.1.4 will be performed if the number of subjects overall with a missing change from baseline value is \geq 5% with the following modifications for cts data: (1) intermittent missing values will be imputed using the Markov Chain Monte Carlo (MCMC) method (Schafer, 1997), and (2) monotone missing values will be imputed using a regression model. Covariate adjustment will be the same as for the primary endpoint for ACQ-5 score and pre-bronchodilator FEV₁. For postbronchodilator FEV₁ and AM PEF, the covariates used in the model will be the same as for the primary endpoint except that baseline pre-bronchodilator FEV₁ will be replaced with baseline post-bronchodilator FEV₁ or baseline AM PEF, depending on the endpoint of interest. ANCOVA without MI will be performed similarly as described above without the imputation of values.

Descriptive statistics for change from baseline to Week 24 along with the LS means, SEs, and corresponding 95% CIs for each treatment group will be presented. Differences in LS means, SEs, corresponding 95% CIs, and p-values for each GB001 group versus placebo will also be constructed from the ANCOVA models.

In addition, each secondary endpoint of change from baseline to Week 24 will be analyzed by MMRM except for change from baseline to Week 24 in post-bronchodilator FEV₁. MMRM will

be performed using a restricted maximum-likelihood (REML)-based approach and an unstructured covariance structure to model within-subject error. The MMRM model will include change from baseline values up to Week 24 as the response variable; the fixed, categorical effects of treatment group, ICS dose (medium or high) at randomization, region, visit, and treatment group by visit interaction; and the cts, fixed covariates of baseline value and baseline value by visit interaction.

Parameters will be estimated using REML with the Newton-Raphson algorithm. Treatment comparisons will be derived from the MMRM. Differences in LS mean changes from baseline, the corresponding 95% CIs, and p-values with Kenward-Roger adjustment (Kenward, 1997) will be provided for comparison for each GB001 group versus placebo. LS means will be reported along with SEs and corresponding 95% CIs, and differences between treatment groups reported with LS means, SEs, corresponding 95% CIs, and p-values.

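### The post-bronchodilator FEV₁ analysis drops the Visit 2 pre-bronchodilator FEV₁ and keeps only a Screening lung-function covariate, giving up precision that may be available at almost no cost

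*Protocol*

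**What the plan says.** - **Endpoint.** Protocol 1.1 and 3 list "Change from baseline to Week 24 in post-bronchodilator" FEV₁ among the secondary endpoints.
- **When it is measured.** In Protocol 1.3 the row "Spirometry post-bronchodilator" is marked at Screening, Week 24 and Early Discontinuation of IP, and not at Randomization. Protocol 8.1.3 agrees on the later readings: "Reversibility in FEV₁ will also be assessed at Visit 9 (Week 24) or the Early Discontinuation of IP visit". The Section 8 procedure list for Visit 2 restricts spirometry to the pre-bronchodilator test.
- **Gap before randomization.** Protocol 4.1.1: "Eligible subjects will enter a Run-in period of a minimum of 2 weeks and a maximum of 6 weeks".
- **Baseline rule.** SAP 8.3.2.1, for every change endpoint in that section except AM PEF: "the baseline value is defined as the last non-missing value on or before the date of the first dose of study treatment". SAP 6.4 fits this. It tabulates post-bronchodilator FEV₁ at Screening only, but pre-bronchodilator FEV₁ at both Screening and Baseline.
- **Model.** The primary model (SAP 8.3.1) has treatment, ICS dose, region, baseline pre-bronchodilator FEV₁ and baseline ACQ-5. For this endpoint, SAP 8.3.2.1 says that baseline pre-bronchodilator FEV₁ "will be replaced with baseline post-bronchodilator" FEV₁.
- **Section 8, other visits.** The list for visits after Visit 2 gives "Spirometry (pre-bronchodilator only", without an exception for Week 24.

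**The concern.** Adjusting a change score for its own baseline is routine. Here, though, that baseline is the older of two available FEV₁ readings. The newer one is already collected at Visit 2 and already used in the primary model. A run-in of up to 6 weeks, in which some subjects may have a treated exacerbation, separates the two. If the Visit 2 reading carries information about Week 24 lung function beyond the Screening reading, leaving it out widens the confidence intervals for no return. Repeated-measures modelling cannot recover that information, because SAP 8.3.2.1 rules out MMRM for an endpoint with one post-baseline timepoint.

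The imputation model is also unclear. Protocol 9.2 assumes 8% dropout. If missingness reaches 5%, ANCOVA with multiple imputation becomes the primary analysis of this endpoint. That imputation is described only as analogous to SAP 8.3.1.1.4, which uses the primary model's covariates. The reader cannot tell whether the Visit 2 FEV₁ stays in it.

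**Working it through.** **1. Which lung-function values enter the model.** The last post-bronchodilator reading on or before first dose is the Screening one. After the substitution the terms are treatment, ICS dose, region, baseline ACQ-5 and Screening post-bronchodilator FEV₁. ACQ-5 is a symptom questionnaire, so the number of lung-function values from randomization is 0.

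**2. Span of the change score.** 24 + 2 = 26 weeks to 24 + 6 = 30 weeks, against 24 weeks for pre-bronchodilator FEV₁ measured from Visit 2.

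**3. Bias.** The Screening value precedes randomization in every arm, so it cannot differ systematically between arms. Only precision and the reading of within-arm change are affected.

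**4. Precision.** The plan states no SD, correlation or power for this endpoint, so there is no figure to reproduce. The correlations below are assumptions, read as holding after adjustment for the other model terms:
- r1, Screening post-bronchodilator with Week 24 post-bronchodilator: 0.85 to 0.90
- r2, Visit 2 pre-bronchodilator with Week 24 post-bronchodilator: 0.80 to 0.86
- r12, Screening post-bronchodilator with Visit 2 pre-bronchodilator: 0.85 to 0.88

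With the baseline in the model, analysing the change or the Week 24 value gives the same treatment difference and residual variance. As a fraction of the Week 24 variance, the residual is 1 − r1² with the Screening value alone. Adding the Visit 2 value cuts it by the squared partial correlation:

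cut = (r2 − r1·r12)² / [(1 − r1²)(1 − r12²)]

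Interval width falls by 1 − √(1 − cut). The corners of the assumed ranges give:

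| r1 | r2 | r12 | Variance cut | Width cut |
|---|---|---|---|---|
| 0.90 | 0.80 | 0.88 | 0.15% | 0.1% |
| 0.90 | 0.80 | 0.85 | 2.3% | 1.2% |
| 0.85 | 0.80 | 0.88 | 4.3% | 2.2% |
| 0.85 | 0.80 | 0.85 | 7.8% | 4.0% |
| 0.90 | 0.86 | 0.88 | 10.8% | 5.5% |
| 0.90 | 0.86 | 0.85 | 17.1% | 9.0% |
| 0.85 | 0.86 | 0.88 | 20.0% | 10.6% |
| 0.85 | 0.86 | 0.85 | 24.6% | 13.1% |

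The two extremes in full:
- Lowest: (0.80 − 0.792)² / (0.19 × 0.2256) = 0.000064 / 0.042864 = 0.0015.
- Highest: (0.86 − 0.7225)² / (0.2775 × 0.2775) = 0.018906 / 0.077006 = 0.2455; 1 − √0.7545 = 0.131.

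Within these ranges the cut rises with r2 and falls with r1 and r12, so the corners are the true limits.

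**5. Price of the covariate.** One degree of freedom among about 480 subjects, roughly 1/480 = 0.2% in variance. At the least favourable corner the change is neutral; elsewhere in the assumed ranges it helps.

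**The case against.** The strongest reply is that the planned ANCOVA is valid and conventional. It adjusts for the endpoint's own baseline, Protocol 9.4.1.2 names no ANCOVA covariates that the SAP could contradict, no power claim attaches to this endpoint, and the gain could be negligible. All of that stands. It limits the point to efficiency but does not defend dropping a covariate that is already collected and costs about one degree of freedom.

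Several stronger readings are tempting, and the documents do not support them:
- *The treatment comparison is biased, or distorted by run-in exacerbations.* The baseline is pre-randomization in all arms. Protocol 4.1.1 and 5.3 also hold back randomization until a subject with a run-in exacerbation has returned to baseline status.
- *The intervals are certainly too wide, by some typical figure such as 8% to 12% of variance.* Some plausible sets of correlations give that, but the same ranges also give 0.15% and 24.6%, and nothing in the documents favours the middle.
- *AM PEF has the same defect.* Its baseline is a 7-day run-in mean that includes Day 1 (SAP 8.3.2.1), so it already carries a lung-function value from randomization.
- *Sites will miss the Week 24 test.* The Section 8 list is a suggested order, is stated to be incomplete, applies only where a procedure belongs to the visit, and sends sites to the Schedule, adherence to which is required. The wording conflict is real, but a missed test would mean departing from the Schedule.

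**Conclusion.** The point holds as a question of efficiency. The ANCOVA for post-bronchodilator FEV₁ uses no lung-function value from randomization, although a suitable one is collected. The between-arm estimate remains unbiased. The possible gain from keeping the Visit 2 value is about 0% to 24.6% of residual variance, or about 0% to 13% of interval width. That range rests wholly on the assumed correlations; blinded pooled data from the trial could narrow it. The unstated Screening baseline and the Section 8 line are minor drafting matters and add nothing to the size of the main point.

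**What to change.** In SAP 8.3.2.1, for post-bronchodilator FEV₁ only, change *replaced with* to *supplemented by*. The model then holds both the Screening post-bronchodilator value and the Visit 2 pre-bronchodilator FEV₁. State that the same two covariates enter the imputation model. Leave the AM PEF model as it is.

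Minor tidying:
- State in the endpoint definition that the baseline for post-bronchodilator FEV₁ is the Screening value.
- Reconcile the Protocol Section 8 spirometry line for other visits with the Schedule and Section 8.1.3 for Visit 9 and Early Discontinuation of IP.

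The cost is a few words in each document and one degree of freedom. No new data are needed, and correlation between the two FEV₁ covariates does not harm the treatment estimate. The model change should be fixed before any unblinding, including that for the interim analysis.
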